## 7.8 Follow-Up Period

All patients will be followed until death or 3 years after registration, whichever occurs first.

# 8.0 TOXICITIES TO BE MONITORED AND DOSE MODIFICATIONS

## 8.1 NCI Common Terminology Criteria for Adverse Events

This study will utilize the CTCAE (NCI Common Terminology Criteria for Adverse Events) Version 4.0 for toxicity and Serious Adverse Event reporting. A copy of the CTCAE Version 4.0 can be downloaded from the CTEP home page (<http://ctep.cancer.gov>). All appropriate treatment areas should have access to a copy of the CTCAE Version 4.0.

## 8.2 Dose Modifications

- a. If patient experiences adverse events that result in the dose modification (including dose delay, reduction, or discontinuation) of ABT-888, or FOLFIRI during a cycle, the patient will complete the planned activities of the cycle as scheduled per [Section 9.0](#) until resuming protocol therapy. If dose interruption is needed, the patient will continue to have study visits as planned. The timing of dose resumption should be at the discretion of the treating physician as long as it is within 4 weeks.
- b. Dose interruptions for events that are clearly not related to the protocol therapy (e.g., underlying cancer, planned surgical procedures, or acute viral illnesses) should not necessitate a dose reduction.
- c. Patients may be treated with antibiotic therapy if they develop severe neutropenia. A new cycle of treatment may not begin until the ANC is  $\geq 1,500/\text{mCL}$ , the platelet count is  $\geq 75,000/\text{mCL}$ , and any treatment-related gastrointestinal toxicity has resolved to  $\leq$  Grade 1. White blood cell growth factors, including biosimilars, must be used per ASCO guidelines (<http://jco.ascopubs.org/content/24/19/3187.full>) and NCCN Guidelines  $\text{\textcircled{R}}$  Myeloid Growth Factors.

([http://nccn.org/professionals/physician\\_gls/pdf/myeloid\\_growth.pdf](http://nccn.org/professionals/physician_gls/pdf/myeloid_growth.pdf)).

- d. No dose re-escalations are permitted. If the patient experiences toxicity requiring a dose reduction, the dose will remain lowered for subsequent cycles.
- e. Where several toxicities with different grades or severity occur at the same time, the dose modification applied should be the greatest reduction applicable.
- f. For toxicities that are considered by the treating physician to be unlikely to develop into serious or life-threatening events (e.g., alopecia, altered taste, etc.), treatment will be continued at the same dose without reduction or interruption. In addition, no dose reductions or interruptions will be required for anemia (non-hemolytic) as it can be satisfactorily managed by transfusions.
- g. The maximum dose delay for any reason is 4 weeks. If the treatment is delayed for > 4 weeks, patients must be removed from protocol therapy.
- h. Dose omitted during a cycle will not be made up.

### 8.3 Dose Modification for ABT-888

#### a. Guidelines

1. **Any event of seizure, regardless of grade or attribution, requires interruption of ABT-888 and discussion with one of the Study Chairs regarding the decision to resume treatment.**
2. ABT-888 will be held until the toxicity(ies) (Grade 3 or 4) recover to ≤ Grade 1 or baseline grade if present at registration. Upon resuming ABT-888 treatment, the dose is to be reduced one dose level as shown. Unless otherwise specified, treatment should continue unmodified for toxicities < Grade 3
3. If a patient begins ABT-888 on Day 1, but subsequently experiences an event requiring delay of the modified FOLFIRI dosing on Day 3, the patient is to stop ABT-888 dosing immediately. Upon resolution of the event, the patient may restart the current cycle by repeating Day 1 and Day 2. For such delays, a new ABT-888 supply will be dispensed to restart the cycle at Day 1.
4. For the purposes of this study, only three dose reductions of ABT-888 are allowed. All dose reductions are permanent. If a dose reduction is required beyond dose level -3, patients should discontinue all protocol therapy. If an intolerable toxicity does not develop, treatment with additional cycles of protocol therapy may be continued indefinitely as long as patient has not met any of the criteria in [Section 7.6](#).
5. ABT-888 may exacerbate neutropenia and thrombocytopenia associated with modified FOLFIRI. ABT-888 dose should be reduced one dose level, as appropriate. **Patients should not receive ABT-888 while fluorouracil infusion and irinotecan are suspended. Skipped doses of ABT-888 during Days 3-7 of each cycle are not made up.**

b. Dose Levels for Treatment Modifications

| Agent   | Starting Dose                      | Level -1                           | Level -2                           | Level -3                          |
|---------|------------------------------------|------------------------------------|------------------------------------|-----------------------------------|
| ABT-888 | 200 mg BID
(400 mg daily total) | 150 mg BID
(300 mg daily total) | 100 mg BID
(200 mg daily total) | 50 mg BID
(100 mg daily total) |

c. Neutrophil Count Decreased

Hold treatment for up to four weeks until recovery to at least Grade 1 (ANC  $\geq$  1,500/mcL). If patient has not recovered to  $\leq$  Grade 1 in four weeks, discontinue treatment. Follow drug specific modifications below for subsequent cycles. In addition, it is recommended that pegfilgrastim 6 mg subcutaneously, be administered with each subsequent dose, on the day of fluorouracil pump discontinuation.

| Toxicity Grade | Modification   |
|----------------|--|
| 3-4            | 1 dose level reduction. At 4 th occurrence, discontinue all protocol treatment. |

d. Platelet Count Decreased

Hold treatment for up to four weeks until recovery to at least Grade 1 (PLT  $\geq$  75,000/mcL). If patient has not recovered to  $\leq$  Grade 1 in four weeks, discontinue treatment. Follow drug specific modifications below for subsequent cycles.

| Toxicity Grade | Modification  |
|----------------|---|
| 3-4            | 1 st occurrence, maintain dose. For subsequent occurrences, continue ABT-888 at 1 dose level reduction. At 5 th occurrence, discontinue all protocol treatment. |

e. Nausea/Vomiting

| Toxicity Grade | Modification   |
|----------------|--|
| 3-4            | Hold treatment for up to four weeks until recovery to at least Grade 1. Continue ABT-888 at 1 dose level reduction. At 4 th occurrence, discontinue all protocol treatment. |

f. Diarrhea

Patients should be instructed in the use of loperamide as treatment for diarrhea. No ABT-888 dose modifications are required for diarrhea. Patients should not receive ABT-888 while fluorouracil infusion and irinotecan are suspended. Skipped doses are not made up.

g. Mucositis

No ABT-888 dose modifications are required for mucositis. Patients should not receive ABT-888 while fluorouracil infusion and irinotecan are suspended. Skipped doses are not made up.

h. Other Non-Hematologic Toxicities

For all other  $\geq$  Grade 3 non-hematologic toxicities not described above, hold ABT-888 and monitor at least weekly. If toxicity resolves to  $\leq$  Grade 1 within four weeks, protocol therapy may be resumed. ABT-888 may be reduced at the treating physician's discretion.

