3-4                    Hold treatment. Check weekly. When resolves to  $\leq$  Grade 1, continue at 1 dose level reduction of fluorouracil and irinotecan up to 3 steps down. At 4th occurrence, discontinue all protocol treatment. NOTE: For patients in Arm 2, discontinue bolus fluorouracil at first occurrence treatment

---

i. Other non-hematologic toxicities

All treatment related non-hematological toxicities  $\geq$  Grade 3 (with the exception of hair loss) must resolve to Grade 1 prior to starting next cycle of therapy. Treatment should continue unmodified for toxicities  $<$  Grade 3.

Toxicity Grade            Modification: Fluorouracil and irinotecan

---

3                        Hold all drugs until resolution to  $\leq$  Grade 1. Then resume treatment at the next lower dose level. Fluorouracil bolus should be discontinued in Arm 2.

4                        Discontinue all protocol treatment

---

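### For treatment-related Grade 4 non-hematologic toxicity with no paragraph of its own, 8.3h lets Arm 1 resume protocol therapy while 8.4i requires all protocol treatment to stop

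*Combined protocol and SAP*

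**What the plan says.** **Section 8.3h (ABT-888, other non-hematologic toxicities).** The scope is Grade 3 or higher, so Grade 4 is included: "non-hematologic toxicities not described above, hold ABT-888 and monitor at least weekly". Attribution is not mentioned. If the toxicity resolves to no worse than "Grade 1 within four weeks, protocol therapy may be resumed".

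**Section 8.3a.2 (ABT-888, general guideline).** Grade 4 is again handled as hold and then resume: "ABT-888 will be held until the toxicity(ies) (Grade 3 or 4) recover to" Grade 1 or the baseline grade.

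**Section 8.4i (FOLFIRI, other non-hematologic toxicities).** The scope is "All treatment related non-hematological toxicities" of Grade 3 or higher, hair loss excepted. The Grade 3 row is hold, then resume one level down. The Grade 4 row is to "discontinue all protocol treatment".

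**Section 8.4 applies to Arm 1.** Section 8.4a says when ABT-888 continues after irinotecan is dropped, and instructions meant only for Arm 2 are marked as such. The 8.4i Grade 4 row carries no arm limit.

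**The concern.** The Grade 4 row of 8.4i is a safety stop. An Arm 1 patient with a treatment-related Grade 4 toxicity covered only by the two catch-all paragraphs, who recovers within four weeks, meets an express permission to resume in 8.3h and a mandatory stop in 8.4i. For the same event in Arm 2 only 8.4i applies, and the patient stops. What is at stake is re-exposure to the full regimen, including the investigational drug, after a toxicity that the protocol elsewhere treats as ending treatment. It also matters how such a continuation is classed afterwards: it is allowed by one paragraph and a deviation from another.

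**Working it through.** The point rests on comparing rules. The plan states no figure for it.

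**1. Trace one case.** Take an Arm 1 patient with a treatment-related non-hematologic toxicity that has no paragraph of its own, recovered to Grade 1 or lower within four weeks.

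| Grade | 8.3h | 8.4i | Compatible on whether therapy resumes? |
|---|---|---|---|
| 3 | may resume | resume one level lower | yes |
| 4 | may resume | stop everything | no |

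The conflict is specific to Grade 4.

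**2. Can the rules be separated by drug?** Not fully. The column heading in 8.4i names only fluorouracil and irinotecan, and the holding step in 8.3h names only ABT-888. But the outcome in each paragraph is stated for protocol therapy or treatment as a whole. Sections 8.3a.5 and 8.4a also bar ABT-888 while the fluorouracil infusion and irinotecan are suspended, so resuming under 8.3h means restarting drugs that 8.4i has stopped.

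**3. Does any other sentence decide?**
- 8.2e (apply the greatest reduction) concerns several toxicities at the same time, not one toxicity under two rules.
- 8.2b covers "Dose interruptions for events that are clearly not related to the protocol therapy" and only removes the need for a dose reduction.
- 7.6b makes unacceptable toxicity a removal criterion but gives no grade.
- 8.3a.4 makes continued treatment depend on no intolerable toxicity and on the 7.6 criteria, again with no grade.
- Section 7.0 refers dosing questions to a study contact and to SWOG Policy 38. Neither that policy nor the text of Section 8.5 was available to me.

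**4. What falls outside the point.** Nausea/vomiting, diarrhea and mucositis have their own paragraphs. Seizure has its own rule in 8.3a.1. Hand-foot skin reaction may resume at Grade 3 or 4 under 8.4g. Events unrelated to treatment are not covered by 8.4i.

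**5. How many patients?** The documents give no Grade 4 rate for these toxicities. The Phase I summary in Section 2.0 pools Grades 3 and 4 and counts treatment-emergent rather than treatment-related events. The only Grade 4 event it names is a neutropenia, which has its own paragraph. Any count is therefore an assumption. Dosing rules bind every treated patient, so the base is planned accrual per arm: 143 / 2 = 71.5, taken as 71. Actual accrual is not given.

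With assumed rate p, the expected number is 71p and the chance of at least one event is 1 − (1 − p)^71. As a check on the formula, p = 5% with the 64 per arm of Section 11.4 gives 1 − 0.95^64 = 96.2%, matching the plan's 96%.

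| Assumed p | Expected among 71 | Chance of at least one |
|---|---|---|
| 0% | 0 | 0% |
| 0.5% | 71 × 0.005 = 0.4 | 1 − 0.995^71 = 30% |
| 1% | 71 × 0.01 = 0.7 | 1 − 0.99^71 = 51% |
| 2% | 71 × 0.02 = 1.4 | 1 − 0.98^71 = 76% |

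These rates only show the range. They count qualifying toxicities. Re-treatments would be no more numerous, since recovery and a decision to resume are also needed.

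**The case against.** The best defence is that a permission and a prohibition can be obeyed together. 8.3h says therapy may resume and 8.4i says it must stop. An Arm 1 patient is under both sections, and stopping breaches neither. 8.4i is also the narrower rule: it covers treatment-related events only and gives Grade 4 its own row. Reading it as a carve-out still leaves 8.3h its Grade 3 events and its unrelated Grade 4 events. The two sections are plainly meant to be applied together. For diarrhea, 8.3f requires no ABT-888 change while 8.4e ends all treatment at the fourth occurrence, and nobody would call that a conflict.

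Most of this stands. It shows which rule should govern and that a compliant course exists. A reader might infer from the clash that sites had no compliant option, or that the two sections cannot be applied jointly; the documents do not support either. What the defence does not remove is the difference between silence and permission. 8.3f is silent on when treatment ends, so 8.4e simply adds to it. 8.3h expressly allows protocol therapy to resume after Grade 4, and that is wrong for treatment-related events if 8.4i is right. The precedence of 8.4i is a sound inference, but the available text does not state it.

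**Conclusion.** The point holds as a minor error in a safety rule. As written, 8.3h permits Arm 1 re-treatment after a treatment-related Grade 4 toxicity for which 8.4i removes the patient. The number affected is unknown and may be zero. The conclusion assumes that nothing in SWOG Policy 38 or Section 8.5 settles precedence, which I could not check.

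Three stronger readings are not supported:
- **That patients were wrongly re-treated.** No such case is reported, and sites had a contact for dosing questions.
- **That the arms were stopped differently in a way that affects the results.** No effect on sample size, power, alpha or the intent-to-treat survival comparison is shown. 8.4i applies to both arms.
- **That there is a second conflict over dose.** 8.3a.2 says "Upon resuming ABT-888 treatment, the dose is to be reduced one dose level as shown", while 8.3h says "ABT-888 may be reduced at the treating physician's discretion". 8.3h can be read as the specific rule, so this is editorial and forms no part of the point.

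Revision #1 states that all patients are off treatment and accrual is permanently closed. The practical value is therefore limited to any reuse of the text and to classing any Arm 1 patient who continued after such an event. Discontinuations are not in doubt, because stopping complied with both rules.

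**What to change.** In 8.3h, limit the resumption sentence to Grade 3 toxicities and to Grade 4 events not related to treatment. Then add: *For treatment-related Grade 4, discontinue all protocol treatment per 8.4i (hand-foot skin reaction: see 8.4g).* The stop already required by 8.4i in both arms is then stated where a site managing ABT-888 will look for it.

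The cost is close to nil: one sentence narrowed and one added, with no new data, analysis or patients.

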8.4 Dose Modification for FOLFIRI

a. Guidelines

Dose modifications for the current cycle and reduction for subsequent cycles should be carried out as shown below. Dose adjustments of irinotecan and fluorouracil infusion may be made independently based on the specific types of toxicities observed as discussed in [Sections 8.4c-i](#). For the purposes of this study, only three dose reductions of FOLFIRI are allowed. If a dose reduction is required beyond dose level -3 for irinotecan, discontinue irinotecan, but continue ABT-888, fluorouracil, and leucovorin. If a dose reduction is required beyond dose level -3 for continuous infusion fluorouracil, discontinue all protocol therapy.

**Patients should not receive ABT-888 while fluorouracil infusion and irinotecan are suspended. Skipped doses of ABT-888 during Days 3-7 of each cycle are not made up.**

Note: The fluorouracil bolus can only be skipped or discontinued.

b. Dose Levels for Treatment Modifications

| Agent                 | Starting Dose           | Level -1                    | Level -2               | Level -3               |
|-----------------------|-------------------------|-----------------------------|------------------------|------------------------|
| Fluorouracil (bolus)* | 400 mg/m    | Discontinue                 | N/A                    | N/A                    |
| Fluorouracil          | 2,400 mg/m  | 1920 mg/m       | 1600 mg/m  | 1360 mg/m  |
| Irinotecan            | 180 mg/m    | 150 mg/m        | 120 mg/m   | 100 mg/m   |
| Leucovorin**          | 400 mg/m    | No dose adjustments allowed |                        |                        |

\* Fluorouracil bolus is only given in Arm 2.

\*\* Leucovorin is always administered at 400 mg/m^2 IV prior to fluorouracil. If fluorouracil 46-48 hour infusion needs to be skipped, leucovorin must also be skipped.

α Patients known to be homozygous for UGT1A1\*28 are recommended to start irinotecan with a 30% dose reduction.

c. Neutrophil Count Decreased

Toxicity Grade Modification:

---

3-4 Hold treatment for up to four weeks until recovery to at least Grade 1. If patient has not recovered to  $\leq$  Grade 1 in four weeks, permanently discontinue treatment. If patient recovers to  $\leq$  Grade 1, one dose level reduction of fluorouracil and irinotecan. At 4th occurrence, discontinue all protocol treatment. NOTE: For patients in Arm 2, discontinue bolus fluorouracil at first occurrence.

---

d. Platelet Count Decreased

Toxicity Grade Modification:

---

3-4 Hold treatment for up to four weeks until recovery to at least Grade 1. If patient has not recovered to  $\leq$  Grade 1 in four weeks, discontinue treatment. If patient recovers to  $\leq$  Grade 1, one dose level reduction of fluorouracil. At 4th occurrence, discontinue all protocol treatment. For the first occurrence, maintain irinotecan dose level and for subsequent occurrences 1 dose level reduction up to 2 steps down. NOTE: For patients in Arm 2, discontinue bolus fluorouracil at first occurrence.

---

e. Diarrhea

Patients should be instructed in the use of loperamide as treatment for diarrhea. Patient should not be retreated with irinotecan until recovery from diarrhea has occurred.

Toxicity Grade Modification

---

3-4 Hold treatment. Check weekly. When resolves to  $\leq$  Grade 1, continue at next lowest dose level. If patient recovers to  $\leq$  Grade 1, one dose level reduction of fluorouracil and irinotecan. At 4th occurrence, discontinue all protocol treatment. NOTE: For patients in Arm 2, discontinue bolus fluorouracil at first occurrence.

---

f. Mucositis

Toxicity Grade Modification: Fluorouracil and irinotecan

---

2-4 Hold treatment. Check weekly. When resolves to  $\leq$  Grade 1, continue at next lowest dose level. NOTE: For patients in Arm 2, discontinue bolus fluorouracil at first occurrence.

---

g. Hand-Foot Skin Reaction

Toxicity Grade    Modification:

---

3-4                    Hold treatment. Check weekly. When resolves to  $\leq$  Grade 1, continue irinotecan at next lowest dose level. Reduce fluorouracil infusion by 1 dose level.

h. Nausea/Vomiting

Toxicity Grade            Modification

---

3-4                    Hold treatment. Check weekly. When resolves to  $\leq$  Grade 1, continue at 1 dose level reduction of fluorouracil and irinotecan up to 3 steps down. At 4th occurrence, discontinue all protocol treatment. NOTE: For patients in Arm 2, discontinue bolus fluorouracil at first occurrence treatment

---

i. Other non-hematologic toxicities

All treatment related non-hematological toxicities  $\geq$  Grade 3 (with the exception of hair loss) must resolve to Grade 1 prior to starting next cycle of therapy. Treatment should continue unmodified for toxicities  $<$  Grade 3.

Toxicity Grade            Modification: Fluorouracil and irinotecan

---

3                        Hold all drugs until resolution to  $\leq$  Grade 1. Then resume treatment at the next lower dose level. Fluorouracil bolus should be discontinued in Arm 2.

4                        Discontinue all protocol treatment

---

8.6 Adverse Event Reporting

Toxicities (including suspected reactions) that meet the expedited reporting criteria as outlined in [Section 16.1](#) of the protocol must be reported to the Operations Office, Study Chair and NCI via CTEP-AERS, and to the IRB per local IRB requirements.

9.0 STUDY CALENDAR

9.1 Arm 1: ABT-888 + mFOLFIRI

Σ

| REQUIRED STUDIES   | PRE
STUDY | Cycle 1 |         | Cycle 2 |         | Cycle 3 |         | Cycle 4 |         | Cycle 5 |          | Ω                      | %                   |
|--|--------------|---------|---------|---------|---------|---------|---------|---------|---------|---------|----------|------------------------|---------------------|
|  |              | Wk
1 | Wk
2 | Wk
3 | Wk
4 | Wk
5 | Wk
6 | Wk
7 | Wk
8 | Wk
9 | Wk
10 | FU
prior to
prog | FU
after
prog |
| PHYSICAL  |              |         |         |         |         |         |         |         |         |         |          |                        |                     |
| History and Physical Exam ◊                                  | X            | X       |         | X       |         | X       |         | X       |         | X       |          | X                      | X                   |
| Weight and Performance Status                                | X            | X       |         | X       |         | X       |         | X       |         | X       |          |                        |                     |
| Disease Assessment   | X            |         |         |         |         |         |         |         |         | X       |          |                        |                     |
| Toxicity Notation  | X            | X       |         | X       |         | X       |         | X       |         | X       |          | X                      |                     |
| Baseline Abnormalities                                       | X            |         |         |         |         |         |         |         |         |         |          |                        |                     |
| LABORATORY π d                             |              |         |         |         |         |         |         |         |         |         |          |                        |                     |
| CBC/Differential/Platelets                                   | X            | X       |         | X       |         | X       |         | X       |         | X       |          |                        |                     |
| CA19-9/CEA \$  | X            | X       |         |         |         | X       |         |         |         | X       |          |                        |                     |
| AST/ALT, total bilirubin, serum albumin,
serum creatinine | X            | X       |         | X       |         | X       |         | X       |         | X       |          |                        |                     |
| Chemistry **   | X            | X       |         | X       |         | X       |         | X       |         | X       |          |                        |                     |
| Pregnancy test △   | X            | X △     |         |         |         |         |         |         |         |         |          | X △                    |                     |
| X-RAYS AND SCANS c                         |              |         |         |         |         |         |         |         |         |         |          |                        |                     |
| CT/MRI for disease assessment                                | X            |         |         |         |         |         |         |         |         | X       |          | X                      |                     |
| SPECIMEN SUBMISSION                                   |              |         |         |         |         |         |         |         |         |         |          |                        |                     |
| Tissue block or slides for TM (required) δ                   | X            |         |         |         |         |         |         |         |         |         |          |                        |                     |
| Archival tissue slides for TM (required) δ                   | X            |         |         |         |         |         |         |         |         |         |          |                        |                     |
| Blood for TM (required) δ                                    | X            |         |         |         |         |         |         |         |         |         |          |                        |                     |
| Tissue for banking (optional) δ                              | X            |         |         |         |         |         |         |         |         |         |          |                        |                     |
| TREATMENT   |              |         |         |         |         |         |         |         |         |         |          |                        |                     |
| ABT-888 ζ  |              | X       |         | X       |         | X       |         | X       |         | X       |          |                        |                     |
| Irinotecan φ   |              | X       |         | X       |         | X       |         | X       |         | X       |          |                        |                     |
| Leucovorin ω   |              | X       |         | X       |         | X       |         | X       |         | X       |          |                        |                     |
| Fluorouracil ξ   |              | X       |         | X       |         | X       |         | X       |         | X       |          |                        |                     |

Click here for [footnotes](#).

